6.2.3 Blinding

Blinding and Unblinding methods: For stimulation sessions, this study utilizes the Cool-B65 A/P coil, which has a built-in position sensor used to ensure that the correct (active or sham) side of the coil faces towards the patient's head. If the coil position is wrong the operator will get a "Flip Coil" prompt on the MagPro screen. To ensure best possible blinding of patients, the current stimulation pads (provided with the Cool-B65 A/P coil) should be used to stimulate the patient's skin and simulate the sensation of active rTMS. When a stimulation session is completed, the session data is stored on both the *Patient Key* and the *Operator Key*. [name] and [name] are authorized to break the blind.

Circumstances for Breaking the Blind: While the safety of the subject always comes first, it is important to seriously consider if unblinding the study randomization assignment is necessary to ensure a subject's safety. In the event of a serious adverse device effect, the PIs will carefully assess whether breaking the blind will critically affect how a subject is treated in response to the adverse effect and whether this knowledge outweighs the implications to the scientific soundness of the study. In the case of most serious adverse effects, the study would be discontinued and symptoms treated symptomatically irrespective of the knowledge of whether the stimulation received was active or sham in nature. In these instances, having this information would not significantly alter the treatment of the adverse effect(s). As an additional safeguard against bias, the Independent Monitoring Committee (IMC) has been charged with making the final

recommendations for breaking the study blind. If the IMC recommends unmasking the study, NCCIH will be contacted and the key to active or sham stimulation will be obtained. Notation regarding the nature of the type of stimulation that the subject had been receiving will be documented in the subject's source document. If the decision to break the blind is made immediately upon learning of the adverse event, this information will be reported to the NCCIH and reviewing IRB at the time of initial adverse event reporting. If the unblinding occurs after the initial reporting, the NCCIH will be notified of the action within ten working days from the time of breaking the blind. The reviewing IRB will be notified according to their reporting guidelines if the decision is made to break the study blind after the initial reporting.

Procedure for Breaking the Blind at Study Completion: To minimize any source of bias, unblinding of the study will not be done until all subjects have completed all study phases. However, unblinding will occur if the Independent Monitoring Committee, consistent with their assigned charter and associated stopping rules, determines that it necessary to do so. At the end of the study *Patient Keys* are returned to the Principal Investigator for data analysis. The MagPro double-blinded research system ensures efficacy, accuracy and consistency. The system comes with a *MagLink* software program specifically developed for data collection in double-blinded studies. The program is used to define the stimulation protocol for each patient (real or sham stimulation).

6.2.4 rTMS Administration (Active and Sham)

- Hypnotic Stroop and Hypnotic Analgesia Scanner Session Days (Same Protocol for Both Days)
 - Evaluation of Adverse Events
 - Motor Threshold Acquisition
 - PEST(90)
 - Visualization and MEP monitor (Electromyography)(132)
 - Neuronavigation
 - Structural Targeting(81)
 - Functional Connectivity Targeting(81)
 - Continuous Theta-Burst Stimulation(17)800 pulses of continuous theta-burst stimulation at 80% rMT (30)
 - 15 minute break(30)
 - 800 pulses of continuous theta-burst stimulation at 80% rMT (30)

- Evaluation of Adverse Events

6.2.5 Post-rTMS (Active and Sham) Evaluations

Post-rTMS Stroop Assessment

Hypnotic Stroop and Non-Hypnotic Stroop Pre-rTMS Scan Session: This session includes all of the post-rTMS behavioral evaluations and scans necessary to compare to the pre-rTMS.

- Hypnotic Induction Profile: This administration of the HIP will serve as the post-rTMS measure for comparison to the pre-rTMS stimulation session.
- Post-TMS Hypnotizability Scan Session (1 hour duration)
 - Structural Acquisition (T1): This structural scan is necessary for several reasons: demonstration that the participant's brain is structurally normal, imaging analysis, and rTMS targeting(81).
 - BOLD fMRI Acquisitions
 - Resting State: This is the scan required for evaluation of the primary endpoint. Individuals with high hypnotizability have been demonstrated to have higher functional connectivity between the dorsolateral prefrontal cortex and the dorsal anterior cingulate cortex (31).
 - Stroop Task: Brain activity while performing conflict tasks has been demonstrated to be different depending on a subject's level of hypnotizability. These scans will demonstrate the subject's functional brain response to the Stroop Task post-rTMS. Functional brain response to the stroop task will be measured following hypnosis (Hypnotic Stroop) and non-hypnosis (Non-Hypnotic Stroop) audio instructions. Randomization of hypnosis and non-hypnosis scan order for each participant will be kept consistent between both pre- and post-rTMS scans. Highly hypnotizable individuals can have a loss of the Stroop Effect with specific post-hypnoitic instruction (119, 120) which correlates with the reduction in neural activity

during conflict (35).

Post-rTMS Analgesia Assessment

Post-rTMS Analgesia Session: This hour-long scan session includes all of the post-rTMS behavioral evaluations and scans necessary to compare to the pre-rTMS.

- Hypnotic Induction Profile: This administration of the HIP will serve as the baseline measure for comparison after the rTMS stimulation session(87).
- Pre-TMS Scans
 - Structural Acquisition (T1): This structural scan is necessary for several reasons: demonstration that the participant's brain is structurally normal, imaging analysis, and rTMS targeting (81).
 - BOLD fMRI Acquisitions
 - Resting State: This is the baseline scan required for the primary endpoint. Individuals with higher hypnotizability have been demonstrated to have higher functional connectivity between the dorsolateral prefrontal cortex and the dorsal anterior cingulate cortex (31).
 - Pain Induction: Using the same moderate thermal pain values identified above, functional brain responses to acute pain, will be measured following hypnosis (Hypnotic Analgesia) and non-hypnosis (Non-Hypnotic Analgesia) audio instructions. Randomization of hypnosis and non-hypnosis scan order for each participant will be kept consistent between both pre- and post-rTMS scans. Hypnotic analgesia during pain induction has been demonstrated to be instruction specific (38, 44) and produce alterations in functional connectivity (123).

MR Spectroscopy Assessment (Optional)

Imaging Procedure

- Structural Acquisition (T1/T2/DWI): A structural scan will be acquired for imaging analysis.
- 1H-MRS Spectroscopy: MEGA-PRESS (GABA/Glx) and NFL-PRESS (Broad spectra) spectroscopy sequences will be acquired bilaterally within the left and right DLPFC using a cutting-edge automated voxel placement procedure that precisely targets the identified connectivity coordinates.
- Resting State fMRI: A BOLD fMRI acquisition will be acquired while the participant is at rest to assess functional connectivity between the insula and DLPFC (bilaterally)

7. SAFETY ASSESSMENTS

7.1 Specification of Safety Parameters

Subject Screening: The *Transcranial Magnetic Stimulation Adult Safety Screen (TASS)* will be utilized to confirm that the potential participant does not have any conditions or devices that would contraindicate rTMS (TBS) administration (101). We will use the MRI screening form to assure that there are no contraindications to MRI scanning (89).

MRI Practices: The CRCs will be trained to ensure that the participant does not enter into the MRI room with any ferromagnetic objects(89).

Motor Threshold Acquisition: The participant's motor threshold will be determined to be accurate through the use of a combination of PEST software (90), visualization, EMG monitoring (91), and neuroimaging of the cortical target of the hand representation. The MT will be attained twice in order to assure accuracy. Each MT acquisition will be performed by a separate TMS operator and the lower of the two MT acquisition trials will be utilized.

Dose Calculation: The dose (80% of the rMT) will be assured to be calculated correctly. Two separate calculations will be done to assure that the dose was correctly calculated.

7.2 Methods and Timing for Assessing, Recording, and Analyzing Safety Parameters

Monitoring of Mental Status during rTMS: All personnel will be familiar with the procedures for subject screening for risk factors prior to treatment, individual risks and potential benefits for specific subjects, appropriate discussion of the risks and potential benefits of study participation as outlined in the informed consent document, the stimulation parameters to be used in this study, monitoring subjects for the potential development of seizures by continuous visual inspection during the course of each treatment session (especially the more subtle signs and symptoms of frontal lobe seizures), and first responder management in the event of a seizure (99). All TMS treaters will be certified in basic life support training(99).

7.3 Adverse Events and Serious Adverse Events

An **adverse event (AE)** is any untoward, undesired, or unplanned event in the form of signs, symptoms, disease, or laboratory or physiological observations occurring in a person who has received stimulation with a TMS device or an MRI scan. The event need not be causally related to the TMS device or the MRI scan.

An AE includes, but is not limited to:

- Any clinically significant worsening of a pre-existing condition;
- An AE occurring from overdose (i.e., a dose higher than that described in the protocol) of a TMS device, whether accidental or intentional;
- An AE occurring from abuse (e.g., use for non-study reasons) of a TMS device;
- An AE that has been associated with a preexisting condition is a clinical condition (including a condition being treated) that is diagnosed before an informed consent form is signed and is documented as part of the subject's medical history.

The questions concerning whether the condition existed before the start of the active phase of the study and whether it has increased in severity and/or frequency will be used to determine whether an event is an intervention-emergent AE (IEAE).

An AE is considered to be intervention-emergent if [1] it was not present when the active phase of the study began and is not a chronic condition that is part of the subject's medical history, or [2] it was present at the start of the active phase of the study or as part of the subject's medical history, but the severity or frequency increased during the active phase. The stimulation phase of the study begins at the time of the first administration of the TMS stimulation (active or sham).

For this study, the treatment follow-up period for adverse events is defined as 30 days following the last study visit.

Follow up will be documented in the subjects study file.

A serious adverse event (SAE) is defined as an AE that:

- Results in death:
- Is life threatening (see below)
- Requires inpatient hospitalization or prolongation of an existing hospitalization (see below)
- Results in a substantial disruption of a person's ability to conduct normal life functions, i.e., the adverse event resulted in a significant, persistent or permanent change, impairment, damage or disruption in the patient's body function/structure, physical activities and/or quality of life
- Necessitates medical or surgical intervention to preclude such impairment
- Results in a congenital anomaly or birth defect

Additionally, important medical events that may not result in death, be life-threatening, or require hospitalization, may be considered SAEs, based upon appropriate medical judgment.

Life threatening refers to immediate risk of death as the event occurred or use or continued use of the device or other medical product might have resulted in the death per the reporter. A life-threatening event does not include an event that, had it occurred in a more severe form, might have caused death, but as it actually occurred, did not create an immediate risk of death.

Hospitalization is to be considered only as an admission. Hospitalization or prolongation of a hospitalization constitutes an AE to be classified as serious.

Note: Hospitalizations planned before the start of the study, for a preexisting condition that has not worsened, do not constitute an SAE (e.g., elective hospitalization for a total knee replacement due to a preexisting condition of osteoarthritis of the knee that has not worsened during the study).

An adverse event of special interest is a device-specific adverse event designated by the PI for transmission in the same time frame as an SAE, even if it does not meet serious reporting criteria. For this protocol, seizure should be reported as an adverse event of special interest.

If there is any doubt whether the information constitutes an SAE, the information should be treated as an SAE for the purpose of this study.

Timing for Reporting of Serious Adverse Events: Any SAE, regardless of causal relationship, must be reported immediately to the Independent Monitoring Committee (within one business

day) by faxing a completed serious adverse event form to the chair of the committee, [name]. Compliance with this time requirement is essential so that the Sponsor may comply with its regulatory obligations. Follow-up information relating to an SAE will be reported to the Independent Monitoring Committee and the NCCIH within one business day after the information is sent to the PI by faxing a completed serious adverse event form to the chair of the committee, [name]. The subject should be observed and monitored carefully until the condition resolves or stabilizes or its cause is identified. Any emergency will be reported to NCCIH and the Independent Monitoring Committee immediately (within one business day) by contacting the [name].

Data Collected to Assess Safety During rTMS: Treaters will be monitoring subjects for the potential development of seizures by continuous visual inspection during the course of each stimulation session (especially the more subtle signs and symptoms of frontal lobe seizures), and first responder management in the event of a seizure. The study personnel have immediate (i.e., within minutes) availability of more sophisticated medical support, including access to an emergency room, in the event that a seizure is not a self-limited event, access to antiepileptic medications, and to life support equipment including oxygen, suction, blood pressure monitoring and cardiopulmonary (CPR) equipment.

Seizure and the following are AE's that will be reported at solicited events:

Body System - Preferred Term	Active TMS (N=165) N (%)	Sham TMS (N=158) N (%)
Eye disorders - Eye pain	10 (6.1)	3 (1.9)
Gastrointestinal disorders - Toothache	12 (7.3)	1 (0.6)
General disorders and site administration conditions - Application site discomfort - Application site pain - Facial pain	18 (10.9) 59 (35.8) 11 (6.7)	2 (1.3) 6 (3.8) 5 (3.2)
Musculoskeletal and connective tissue disorders - Muscle twitching	34 (20.6)	5 (3.2)
Skin and subcutaneous tissue disorders - Pain of skin	14 (8.5)	1 (0.6)

Table 2: Adverse events with an incidence in active rTMS at a rate of > 5% and at least 2x sham in the safety exposure study population. These symptoms have occurred only during and not after rTMS administration.

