There is no known risk of seizure with the currently stated parameters (17, 24). In order to have a seizure from inhibitory rTMS (cTBS), one must receive stimulation that is at or greater than 100% of the participant's motor threshold (MT) (24). The MT is reflective of stimulation output necessary to cause a neuronal depolarization (83). Without neuronal depolarization, seizure from rTMS has not been demonstrated to occur. The traditional rTMS parameters have resulted in seizure because these require 120% of the MT (84). cTBS has been demonstrated to modulate the brain with less than 100% motor threshold (17). Only one case of cTBS has resulted in seizure and this case was related to using 100% MT (24, 85). cTBS has been utilized safely in children with no incidence of seizure (21, 22) and has been suggested to be similar risk to single and paired pulse TMS (21), which has been rated as minimal risk for children (23). Inhibitory rTMS (cTBS) will be administered in the Stanford Center for Cognitive and Neurobiological Imaging and outside the scanner. Benzodiazepines will be on hand in the event of seizure and the participant will be immediately transferred to the Emergency Room. Because of the fixed nature of the stimulation dose, there will be no modification to the stimulation parameters. The dose of inhibitory rTMS (cTBS) is personalized for each participant through the use of resting motor threshold acquisition (90).

Hearing Risk: There is the potential risk of alteration in auditory threshold secondary to exposure to rTMS. As a result of the rapid changes in the magnetic field during rTMS administration, the coil produces an audible, high-energy clicking sound, which may be associated with temporary increases in auditory threshold. During previous studies with the rTMS approaches, all subjects were required to use hearing protection at a protection rating of ≥ 30 db. No change in hearing was found with air conduction threshold testing in the two randomized clinical studies when this method of ear protection was used. All participants will be asked to use earplugs for this study.

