Other side effects of TMS: Prophylactic use of acetaminophen or ibuprofen will be allowed for subjects reporting sensations at or near the stimulation site, which are uncomfortable or painful. Participants reporting headaches during or following study stimulation session will be encouraged to take acetaminophen or ibuprofen prior to the stimulation session. All subjects will be monitored, and appropriate treatment will be recommended including the possibility of discontinuing the next scanner day. Any other potential side effects will be managed symptomatically with treatment(s) deemed appropriate by the study site Principal Investigator. All symptomatic interventions will be recorded in the subject's case file and, if applicable, adverse event CRF.

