An AE or SAE can occur from the time that the subject signs the informed consent form to 7 days from the subject's last study visit regardless of relationship to the protocol or TMS device. This includes events that emerge during the pre-study screening phase. All AEs and SAEs will be recorded on source documents and recorded on the subject's case report forms (CRFs). All AEs and SAEs that occur after the pre-study screening period will be recorded on the subject's CRFs, which will be provided to the NCCIH. The Independent Monitoring Committee (IMC) will instruct the Principal Investigator to follow all AEs, SAEs, and other reportable events until the event has subsided or values have returned to baseline, or in case of permanent impairment, until the condition stabilizes. The Investigator will provide all relevant documentation pertaining to an SAE (e.g., additional laboratory tests, consultation reports, discharge summaries, postmortem reports, etc.) to the IMC and NCCIH in a timely manner. Reports relative to the subject's subsequent course will be submitted to the IMC and NCCIH until the event has subsided or, in case of permanent impairment, until the condition stabilizes. Other information reportable to the IMC and NCCIH, while not meeting the definition of an AE, is reportable to NCCIH and the IMC with the timeliness of an SAE.

This includes:

- Seizure

- Pregnancy occurring during the study period in which the subject was exposed to the TMS device;
- Overdose (e.g., a dose higher than that prescribed by a healthcare professional for clinical reasons) with or without AEs;
- Abuse (e.g., use for non-clinical reasons) with or without an AE;
- Inadvertent or accidental exposure with or without an AE;
- Device malfunction that would likely result in death, serious injury or other significant adverse event.

At each required study visit, all AEs that have occurred since the previous visit will be recorded in the adverse event record of the subject's CRF. The information recorded should be based on the signs or symptoms detected during the physical examination and clinical evaluation of the subject.

In addition to the information obtained from those sources, the subject should be asked the following nonspecific question: "How have you been feeling since your last visit?" Signs and symptoms will be recorded using standard medical terminology.

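### Headache and, more weakly, hearing change are named as TMS harms but are not on the solicited adverse-event list in 7.3, so they may be counted less completely than the listed local sensations

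*Combined protocol and SAP*

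**What the plan says.** All references are to the combined protocol and SAP.

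Section 7.3 introduces the list with "Seizure and the following are AE's that will be reported at solicited events" and follows it with a table of seven preferred terms: eye pain, toothache, application site discomfort, application site pain, facial pain, muscle twitching and pain of skin. The caption gives the selection rule, "Adverse events with an incidence in active rTMS at a rate of > 5% and at least 2x sham", and adds: "These symptoms have occurred only during and not after rTMS administration". The table's denominators (165 active, 158 sham) belong to an earlier study, not to this trial's two arms of 50.

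Section 5.1 names two harms that are not on the list. Under hearing: "There is the potential risk of alteration in auditory threshold secondary to exposure to rTMS". Under other side effects: "Participants reporting headaches during or following study stimulation session will be encouraged to take acetaminophen or ibuprofen prior to the stimulation session".

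For adverse events in general, 7.4 has all events since the previous visit recorded at each required visit, from examination and clinical evaluation and from one open question, "How have you been feeling since your last visit". Section 6.2.4 places an adverse-event evaluation before and after the cTBS trains on both stimulation days without saying what it asks. The schedule in 6.1 marks adverse events at every in-person visit and has no headache or hearing item.

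**The concern.** A table filtered on excess over sham describes effects attributable to active stimulation. It is a less natural source for deciding what to ask every participant, because a harm common in both arms can fail the ratio test. Events that begin after stimulation are also outside what its caption describes. Headache and hearing change fit that description: the protocol expects headache during or after a session, and the sham side of the coil is acoustically matched (section 3), so any effect of noise could occur in both arms.

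Prompted and unprompted reports are not collected on the same footing. If local sensations are asked about by name and headache is not, the two counts in the safety tables are not comparable. The monitoring committee, which under 9.5 reviews adverse events at least every six months and for which adverse effects are a stopping ground, would see an unevenly collected profile.

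**Working it through.** **1. Reproduce the table in 7.3.** Rate = count/165 (active) or count/158 (sham); ratio = active rate/sham rate, from unrounded rates.

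| Term | Active | Sham | Ratio |
|---|---|---|---|
| Eye pain | 10/165 = 6.1% | 3/158 = 1.9% | 3.19 |
| Toothache | 12/165 = 7.3% | 1/158 = 0.6% | 11.49 |
| Application site discomfort | 18/165 = 10.9% | 2/158 = 1.3% | 8.62 |
| Application site pain | 59/165 = 35.8% | 6/158 = 3.8% | 9.42 |
| Facial pain | 11/165 = 6.7% | 5/158 = 3.2% | 2.11 |
| Muscle twitching | 34/165 = 20.6% | 5/158 = 3.2% | 6.51 |
| Pain of skin | 14/165 = 8.5% | 1/158 = 0.6% | 13.41 |

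All 14 printed percentages reproduce, and every term passes both parts of the rule. The printed list is what the caption says it is.

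**2. What the rule leaves out.** With sham rate s, a term needs an active rate above 5% and of at least 2s. At s = 10% active must reach 20%; at 20%, 40%; at 30%, 60%. Events common in both arms are the ones most easily lost. Sham occurrence alone does not exclude a term: all seven occurred on sham, at 0.6% to 3.8%.

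**3. Harms named in 5.1 against the list in 7.3.**
- Seizure: on the list.
- Discomfort or pain at the stimulation site: on the list, as application site discomfort and pain.
- Headache during or after stimulation: not on the list.
- Change in auditory threshold: not on the list.

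So two of the four are not solicited.

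**4. How the two unlisted harms are collected.** The routes are examination, clinical evaluation and the open question at visits (7.4), the evaluations around cTBS (6.2.4), and continuous monitoring by coordinators and the principal investigator (7.4). None of these, as written, asks about headache or hearing by name.

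**5. After the last session.** The open question looks back to the previous visit. An event starting after the first stimulation day can be picked up on the second. For an event starting after the second there is no later visit, because section 3 plans no follow-up beyond the two scan sessions. Yet 7.3 and 7.5 set an adverse-event follow-up of 30 days after the final visit, and 7.4 sets 7 days. The three statements do not agree, and none says how a late event would be elicited.

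**6. Size.** Reported rate = true rate × proportion captured. The documents give neither factor for headache or hearing, so no shortfall can be calculated.

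**The case against.** The strongest reply is that nothing is lost. All adverse events are to be recorded at every visit, with evaluations on either side of stimulation. Both arms are blinded and use the same method, so the comparison of arms is not distorted by unequal questioning. For hearing, 5.1 asks all participants to wear earplugs and reports no change on threshold testing in two earlier studies with ear protection; a symptom question might not detect a temporary threshold shift in any case. The case report forms (6.2.2) and the stimulation manual (Appendix 2) are not in the documents reviewed and may already carry these items. The caption's remark on timing describes the source data; it does not restrict what this trial collects.

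Most of this stands and limits the point to completeness and consistency of counting. It does not explain why two harms that the protocol names are absent from the list that it defines as solicited.

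A reader might infer more than the documents support:
- *That the filter removes any harm seen on sham.* It does not (step 2). Nor does any document show that headache was in the source data and was filtered out.
- *That these events are left to spontaneous report.* The routes in step 4 rule this out. They are not specifically prompted.
- *That the gap hides who took analgesics.* Section 6.1 schedules current and concomitant medications on both scan days, and 5.1 has symptomatic treatments recorded in the case file.
- *That two of three named harms are missed, with only seizure covered.* This overlooks stimulation-site discomfort, which 5.1 names and 7.3 solicits.

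**Conclusion.** The point holds in a limited form. Headache and, more weakly, hearing change are named as TMS harms in 5.1, are absent from the solicited list in 7.3, and are collected only by routes that do not ask about them. Their counts may therefore be less complete than those for the listed local sensations, and headache that begins after the final session has no stated prompt. Headache carries the finding.

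It would be tempting to say that these harms will be under-counted by some stated amount. The documents do not support that: under-counting is a plausible risk of unknown size. The conclusion assumes that the unseen forms and manuals do not already contain the two items. It affects safety description, not the primary analysis, and is a cheap improvement rather than a flaw that threatens the trial.

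**What to change.** In 7.3, define the solicited list as seizure, the seven table terms, headache, and change in hearing or ringing in the ears. State that all items are asked in the same words in both arms at the evaluations already placed before and after cTBS in 6.2.4, and that onset is recorded as during or after stimulation. Keep the open question in 7.4 for everything else.

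Reconcile the 7-day window (7.4) and the 30-day window (7.3, 7.5) with each other and with the statement in section 3 that there is no follow-up beyond the scan sessions. Ask the same items at whatever adverse-event follow-up results; without this, the added items would still miss events that start after the second stimulation day.

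The cost is two more items at evaluations that already take place, with no new procedure; any further contact depends on how the windows are reconciled. The downside is that prompted reporting raises the stated counts in both arms, so these rates should be labelled as solicited wherever they are presented.
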